9. REFERENCES

None.

10. APPENDICES

Appendix 1. SAS CODE FOR ANALYSES

- An example of the PROC Mixed code is provided below for ANOVA:

```
proc mixed data = tab.pk covtest alpha=0.1;
  class group;
  model l&var = group / S covb alpha=0.1 CL DDFM=KR;
  repeated/type=un subject=subjid group=group R;
  lsmeans group;
  estimate 'Moderate vs Normal'      group 1 0 -1 0;
  estimate 'Mild vs Normal'         group 0 1 -1 0;
  estimate 'Severe vs Normal'       group 0 0 -1 1;
  ods output lsmeans = lsmeans&var;
  ods output solutionf = solution&var;
run;

/* Letter assignments for group within the estimate statement above are as follows;

A = Moderate (Test);
B = Mild (Test);
C = Normal (Reference);
D = Severe (Test) */;
```

- Linear Regression Example code (Relationship between PK parameters (CL/F or CL_r and V_z/F) and renal function (eGFR):

```
Proc glm data=tab.pk
  class trt;
  model &var= trt &var1/ solution clparm alpha=0.1;
  ods 'FitStatistics' out=Rsq&var;
  ods 'Modelanova' out=tst&var;
  ods 'Parameterestimates' out=pe&var;
run;
```

Notes:

&var = [CL/F or CL_r] / V_z/F
&var1 = eGFR

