For both Parts 1 and 2: All participants in both normal and renal impairment groups will provide informed consent and undergo Screening evaluations to determine their eligibility. Participant screening for participation in this study will consist of 2 CRU outpatient visits not more than 14 days apart (but at least 3 days apart), with the first screening visit occurring within 28 days prior to administration of investigational product. An eGFR value for group placement (provided stable renal function is still demonstrated) will be obtained by the average of the 2 screening values (using the CKD-EPI equation). If the renal function stability criterion is met but the renal function classification category changes between S1 eGFR and the average of the S1 and S2 eGFRs, the eGFR measurement at Day -1 will also be used to determine the appropriate group classification category using an average of all 3 GFR values, to determine whether the participant will be eligible for enrollment.

Eligible participants will be admitted to the CRU on Day -1 (at least 12 hours prior to the dosing of PF-07321332 on Day 1) and will be confined in the CRU until Day 3. If participant meets all screening criteria at S2 visit, and Day -1 visit can be performed immediately, the participant may be admitted to the unit at conclusion of S2 visit.

On the evening of Day -1, participants will receive a single 100 mg dose of ritonavir (-12 hr relative to PF-07321332 on Day 1). On the morning of Day 1, the participants will receive a 100 mg single dose of PF-07321332 with a 100 mg dose of ritonavir after a fast of at least 10 hours. No food will be allowed for at least 4 hours post-dose. Ritonavir, 100 mg, will continue to be dosed at 12 and 24 hours post PF-07321332 dosing to ensure maintenance of the PK boosting effect. Serial blood and urine samples at specified intervals (as per [SoA](#)) will be collected for 48 hours post-dose for plasma and urine PK assessments, prior to discharge from the CRU on Day 3. The eGFR value determined on Day -1 will be used for PK analysis.

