9.3. Statistical Analyses

The SAP will be developed and finalized before any analyses are performed and will describe the analyses and procedures for accounting for missing, unused, and spurious data. This section is a summary of the planned statistical analyses of the primary and secondary endpoints.

ANOVA will be used to compare the natural log transformed AUC_{inf} (or AUC_{last} if AUC_{inf} cannot be reliably estimated) and C_{max} for PF-07321332 between normal renal function group (Reference) and each impaired renal function group separately as applicable (Test). Estimates of the adjusted mean differences (Test-Reference) and corresponding 90% CIs will be obtained from the model. The adjusted mean differences and 90% CIs for the differences will be exponentiated to provide estimates of the ratio of the adjusted geometric means (Test/Reference) and 90% CIs for the ratios. If substantial differences in demographic characteristics between healthy and impaired participants are observed, weight and age may be explored as covariates.

Box and whisker plots for individual participant parameters (AUC_{inf} and C_{max}) will be constructed by renal function group and overlaid with geometric means.

For summary statistics and median/mean plots by sampling time, the nominal PK sampling time will be used. For individual participant plots by time, the actual PK sampling time will be used.

Linear regression will be used to analyze the potential relationship between appropriate PK parameters (CL/F or CL_r , and V_z/F) and renal function (eGFR). Estimates of the slope and, intercept, together with their precision (90% CI), and the coefficient of determination will be obtained from the model.

Plots of PK parameters (CL/F or CL_r , and V_z/F) versus renal function (eGFR) will be constructed. A regression line and 90% confidence region for the PK parameters and eGFR will be included if appropriate. Vertical lines for the renal function group cut-off values will also be presented on the plots. Different symbols will be used to identify participants from different renal function groups.

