Each enrolled participant will receive a single 100 mg dose of PF-07321332 administered orally in combination with the PK boosting agent ritonavir administered as a 100 mg dose at -12, 0, 12, and 24 hours relative to PF-07321332 dosing.

The total planned duration of participation, from the Screening visit to the last Follow-up phone call, is approximately up to 9 weeks.

Calculation of eGFR

The following CKD-EPI equation will be used to calculate eGFR ($S_{cr, std}$ denotes serum creatinine measured with a standardized assay for serum creatinine):

If female and SCr is ≤ 0.7 mg/dL:

$$eGFR (\text{mL/min}/1.73 \text{ m}^2) = 144 \times (S_{Cr, \text{std}}/0.7)^{-0.329} \times 0.993^{\text{age}} (\times 1.159, \text{ if Black})$$

If female and SCr is > 0.7 mg/dL:

$$eGFR (\text{mL/min}/1.73 \text{ m}^2) = 144 \times (S_{Cr, \text{std}}/0.7)^{-1.209} \times 0.993^{\text{age}} (\times 1.159, \text{ if Black})$$

If male and SCr is ≤ 0.9 mg/dL:

$$eGFR (\text{mL/min}/1.73 \text{ m}^2) = 141 \times (S_{Cr, \text{std}}/0.9)^{-0.411} \times 0.993^{\text{age}} (\times 1.159, \text{ if Black})$$

If male and SCr is > 0.9 mg/dL:

$$GFR (\text{mL/min}/1.73 \text{ m}^2) = 141 \times (S_{Cr, \text{std}}/0.9)^{-1.209} \times 0.993^{\text{age}} (\times 1.159, \text{ if Black})$$

Note that the value of eGFR, which is directly obtained from the laboratory or calculated using the equation above, is generally normalized to an average body size of 1.73 m^2 for diagnosis, prognosis and treatment of renal disease. In terms of clearance of renally filtered drugs (including secreted drugs), renal elimination capacity is related to absolute GFR in mL/min. To use the CKD-EPI-derived, BSA-adjusted value of eGFR to obtain absolute GFR (mL/min) for renal disease classification or participant assignment into different renal disease groups, this value should be multiplied by the individual participant's BSA (ie, measured BSA/ 1.73 m^2). The BSA of an individual can be calculated by the following formula as described below:

$$BSA = (Weight^{0.425} \times Height^{0.725}) \times 0.007184$$

In summary, GFR in mL/min calculated as below will be used for renal impairment group placement:

Step 1: Obtain the CKD-EPI-derived eGFR:

Step 2: Convert the CKD-EPI-derived, BSA-adjusted eGFR obtained above to absolute GFR (mL/min) for eligibility assessment using the following equation:

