6.4. Covariates

None.

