8. STATISTICAL METHODOLOGY AND STATISTICAL ANALYSES

8.1. Statistical Methods

8.2. Statistical Analyses

ANOVA will be used to compare the natural log transformed AUC_{inf} (or AUC_{last} if AUC_{inf} cannot be reliably estimated) and C_{max} for PF-07321332 between normal renal function group (Reference) and each impaired renal function group separately as applicable (Test). Estimates of the adjusted mean differences (Test-Reference) and corresponding 90% CIs will be obtained from the model. The adjusted mean differences and 90% CIs for the differences will be exponentiated to provide estimates of the ratio of the adjusted geometric means (Test/Reference) and 90% CIs for the ratios. If substantial differences in demographic characteristics between healthy and impaired participants are observed, weight and age may be explored as covariates.

Box and whisker plots for individual participant parameters (AUC_{inf} and C_{max}) will be constructed by renal function group and overlaid with geometric means.

For summary statistics and median/mean plots by sampling time, the nominal PK sampling time will be used. For individual participant plots by time, the actual PK sampling time will be used.

Linear regression will be used to analyze the potential relationship between appropriate PK parameters (CL/F or CL_r , and V_z/F) and renal function (eGFR). Estimates of the slope and, intercept, together with their precision (90% CI), and the coefficient of determination will be obtained from the model.

Plots of PK parameters (CL/F or CL_r , and V_z/F) versus renal function (eGFR) will be constructed. A regression line and 90% confidence region for the PK parameters and eGFR will be included if appropriate. Vertical lines for the renal function group cut-off values will also be presented on the plots. Different symbols will be used to identify participants from different renal function groups.

Residuals from the model will be examined for normality and the presence of outliers via visual inspection of plots of residuals vs predicted values and normal probability plots of residuals but these will not be included in the clinical study report. If there are major deviations from normality or outliers then the effect of these on the conclusions will be investigated through alternative transformations and/or analyses excluding outliers. Justification for any alternative to the planned analysis will be given in the report of the study.

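### The SAP's example regression code adds an undefined class variable `trt` that SAP 8.2 does not plan; if `trt` is renal cohort, the 90% CI for the eGFR slope becomes several times wider

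*SAP*

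**What the plan says.** **Text.** Protocol 9.3 states: "Linear regression will be used to analyze the potential relationship between appropriate PK parameters", naming CL/F or CLr, and Vz/F, with eGFR as the measure of renal function. SAP 8.2 repeats this and lists the output: "Estimates of the slope and, intercept, together with their precision (90% CI), and the coefficient of determination will be obtained from the model". For the plot it says: "A regression line and 90% confidence region for the PK parameters and eGFR will be included if appropriate". Renal function group enters only as vertical cut-off lines and as a plotting symbol: "Different symbols will be used to identify participants from different renal function groups". Neither text puts a group or treatment term in this regression. The entry under SAP "6.4. Covariates" is None.

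**Code.** The PROC GLM example in SAP Appendix 1 declares `trt` in the CLASS statement and then has "model &var= trt &var1/ solution clparm alpha=0.1". The Notes below it define only `&var` (the PK parameter) and `&var1` (eGFR). The PROC MIXED example just above it reads the same dataset and calls renal cohort `group`.

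**Related facts.** SAP 2.1 gives one planned regimen for everyone: "Each enrolled participant will receive a single 100 mg dose of PF-07321332 administered orally in combination with the PK boosting agent" ritonavir. Cohorts are cut on eGFR (SAP Table 1) using the average of the screening values, whereas Protocol 4.1 says: "The eGFR value determined on Day -1 will be used for PK analysis".

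**The concern.** The text describes a simple regression and the code fits an analysis of covariance. What the code does depends on a variable that the SAP leaves undefined.

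A true treatment variable would have one level under the planned regimen and would do nothing. A multi-level `trt` is most naturally the renal cohort, although the SAP does not say so. Cohort is a coarse version of eGFR. Adjusting for it removes the between-cohort contrast that the design sets up and leaves the slope to the eGFR variation inside each band. Three of the planned outputs would then differ from what SAP 8.2 promises:

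- the slope's CI would be much wider;
- the intercept row that GLM prints would be that of the last class level, not of a common line;
- R² would include variation explained by cohort.

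This is the planned analysis of clearance against continuous renal function, in a study whose findings are meant to support dosing recommendations.

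**Working it through.** The documents give no precision or power for this regression, so there is no figure of the plan's own to reproduce. The question is how much the slope's interval changes between the two models.

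**Formula.** With common residual SD σ, SE(slope) = σ/√SS_total for the planned model and σ/√SS_within when cohort is in the model, where SS is the sum of squares of eGFR. σ cancels in the ratio:

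CI width ratio = √(SS_total/SS_within) × t(0.95, N−k−1)/t(0.95, N−2), with k cohorts.

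**Inputs from the documents.** 8 per cohort; cut-offs at 30, 60 and 90 mL/min (Table 1 of both documents).

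**Assumptions (not in the documents).** Lower limit 15 for severe, upper limit 120 for normal, eGFR uniform within bands.

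**Analytic result, four cohorts.**
- SS_within = 7 × (30² + 30² + 30² + 15²)/12 = 1,706.
- Band means are 22.5, 45, 75 and 105, with overall mean 61.875. SS_between = 8 × (39.375² + 16.875² + 13.125² + 43.125²) = 8 × 3,867.2 = 30,938.
- SS_total = 1,706 + 30,938 = 32,644, so the within-band share is 1,706/32,644 = 5%.
- √(32,644/1,706) = 4.37. The t quantiles (27 and 30 df) differ by less than 1%, so the CI ratio is 4.4.

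**Simulation of both fits.** Further assumptions: clearance = 3.5 + 0.04 × eGFR L/h and CV 30%.

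| Quantity | eGFR only (SAP 8.2) | With cohort as `trt` |
|---|---|---|
| Mean slope | 0.040 | 0.040 |
| 90% CI half-width | 0.017 | 0.073 |
| Median R² | 0.35 | 0.42 |

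The half-widths are rounded; the ratio before rounding is 4.4. A CV of 20% or 40% barely changes it.

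**Sensitivity of the width ratio.**

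| Reading of `trt` and scenario | Ratio |
|---|---|
| One-level treatment | 1.0 |
| Two-level dose (severe against the rest), four cohorts | about 1.4 |
| Cohort: four cohort combinations, no screening-to-Day -1 difference | 3.2 to 5.2 |
| Cohort: same combinations, 10% difference | 2.5 to 3.9 |
| Cohort: eGFR piled at band edges, 15% difference (lowest tried) | 2.0 |
| Cohort: eGFR in the middle half of each band, no difference (highest tried) | 10.2 |

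The four combinations are all four cohorts; moderate, mild and normal; moderate and normal; and severe, moderate and normal. For the two-level dose, SS_within is 131 (severe) plus 1,575 + 14,400 (the other three pooled) = 16,106, and √(32,644/16,106) = 1.42.

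A separate calculation with other eGFR limits (lower 5 to 15, upper 110 to 150) gave 2.7 to 5.5 across cohort combinations with no screening-to-Day -1 difference. In its illustration (slope 0.05, residual SD 1.5, four cohorts of 8, limits 15 and 120), the share of slope intervals excluding zero fell from about 100% to 38%.

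**The case against.** The strongest reply is that the harm rests on a guess about `trt`. The SAP carries other leftover wording that does not fit a single-dose, non-randomized study, such as randomization, washout and period, so `trt` may simply be template residue with one level and no effect. The ANOVA code already has a name for cohort, `group`, which weighs against `trt` being cohort. A third reading also exists: Protocol 6.5 allows a reduced dose in Part 2, so a treatment variable could have two levels, and the widening would be only about 1.4 times. These points stand. They make the size conditional, but they do not remove the mismatch.

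It can also be said that this is labelled example code, that it needs syntax edits before it will run, and that the planned single regression line would alert a programmer. That is fair, but it is the only implementation the SAP gives for this regression, and repairing the syntax would not show that `trt` should go.

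SAP 6.4 is weak support: its entry of None omits eGFR too, and SAP 8.2 allows weight and age to be explored in the ANOVA. The case rests on SAP 8.2 set against Appendix 1.

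Finally, no hypothesis or decision rule depends on this regression, and it can be rerun without new data. That limits the seriousness. It is not a reason to leave the conflict in place.

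**Conclusion.** The concern holds. The code in Appendix 1 does not fit the model in SAP 8.2 and Protocol 9.3, and that part needs no assumption. The text is right and the code should follow it.

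The consequence depends on `trt`. It is nil for a one-level variable, about 1.4 times for a two-level dose, and several times for cohort. In the cohort case the direction is certain, because cohorts are bands of eGFR. The size depends on eGFR limits, within-band distribution and Day -1 variability that the documents do not give. Since placement uses screening eGFR and the PK analysis uses the Day -1 value, 2.5 to 3.9 is a more realistic range than the 4.4 obtained with no difference between them, although the 10% behind that range is itself assumed.

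The slope remains unbiased under linearity, and the primary ANOVA of AUCinf and Cmax is untouched. This should be fixed before programming, as a point on a supporting analysis.

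**What to change.** Delete the `class trt` statement and remove `trt` from the model, so that it reads `model &var = &var1 / solution clparm alpha=0.1;`. Keep cohort only as the plotting symbol. This restores the SAP 8.2 model whichever meaning of `trt` was intended. If the sponsor does want a group term, it should define the variable and justify it in SAP 8.2, with the intercept and R² described accordingly.

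Three small edits can go in at the same time: state in the Notes that `&var1` is the Day -1 eGFR, as Protocol 4.1 already requires; add the semicolon after `data=tab.pk`, unless it was lost in PDF extraction; and write the ODS lines in the `ods output` form used in the PROC MIXED step.

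The cost is an edit to the SAP appendix. Design, data collection and the primary analysis do not change.
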